**Figure 3-1 Study Design**

All infusions will take place at the investigative site in a suitable facility. Patients will remain at the clinic for at least 2 hours after the end of the infusion. The investigator will discharge the patient following satisfactory monitoring of safety parameters.

Safety assessments will include physical examinations, ECGs, vital signs, standard clinical laboratory evaluations, hematology, blood chemistry and urinalysis. Adverse Events (AEs) will be monitored throughout the study duration with special interest to infections. PK/PD and biomarkers will be evaluated during the study.

Details of the study procedures and samplings are provided in the Assessment Schedule ([Table 8-1](#)).

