### 3 Investigational plan

#### 3.1 Study design

This is a randomized double-blind, placebo controlled, non-confirmatory study to preliminarily evaluate the safety, tolerability, PK/PD, and efficacy of IV CFZ533 administered every four weeks (q4w) over a 24 week treatment period in patients with moderate to severe MG. The investigational drug or placebo will be administered in addition to standard of care therapy for MG.

Patients should remain on their standard of care therapies and the dose should be maintained at a constant level during the study ([Section 4.1](#) and [Section 6.10](#)). For patients that are receiving corticosteroids at baseline, a predefined steroid tapering will be allowed after achievement of minimal manifestations (MM) state ([Jaretzki et al 2000](#)).

[figure not shown]
Patients on cholinesterase inhibitors (CI) should remain on stable doses throughout the study, but CIs should not be taken for at **least 12 hours prior** to QMG and MG composite testing at each visit, in order to reduce fluctuations in performance on functional tests due to the temporary symptomatic effects associated with CI use.

For each patient, there will be two screening visits. Most of the screening assessments are done during Screening Visit 1 (Day -28 to Day -8), while Screening Visit 2 (Day -7 to Day -3) is performed to collect a blood sample to allow laboratory results (chemistry, hematology, and pregnancy test, if applicable) to be available prior to randomization on Day 1. All laboratory results, including the MG autoantibodies diagnostic test performed at screening, must be available prior to dosing (Day 1-Visit 3) and meet eligibility criteria. Once continued eligibility is confirmed, patients will be assigned a randomization number at Day 1 and receive CFZ533 or placebo via a 2-hour intravenous infusion. Patients will be dosed every four weeks (q4w) according to their randomization for a total of 6 doses on Day 1 ± 2 (Week 1), Day 29 ± 2 (Week 5), Day 57 ± 2 (Week 9), Day 85 ± 2 (Week 13), Day 113 ± 2

(Week 17) and Day 141 ± 2 (Week 21). The treatment period (24 weeks) will be followed by a safety follow-up period of other 24 weeks. The duration of the entire study including screening will be approximately 52 weeks.

An overview of the study design is given in [Figure 3-1](#):

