### 3.6 Risks and benefits

It is not known if there could be a benefit to patients from treatment with CFZ533.  
Corporate Confidential Information

Corporate Confidential Information

The risk to subjects in this trial will be minimized by adherence to the inclusion/exclusion criteria, close clinical monitoring, and targeted monitoring/follow-up visit safety assessments.

Corporate Confidential Information

Hypersensitivity or infusion reactions can manifest with itching, flushing, headache, nausea/vomiting, hypotension, urticaria, bronchospasm, or angioedema. No such events were found in the Phase 1 study with CFZ533. In this study, CFZ533 will be administered as a 2-hour infusion where such hypersensitivity reactions can still occur. Subjects will be monitored up to 4 hours after the end of the infusion at each visit.

Subjects treated with CFZ533 may be at an increased risk of infection.  
Corporate Confidential Information

Administration of CFZ533 is expected to result in immunosuppression, with a decreased capacity to mount a response to novel immunogens requiring T cell-dependent B cell activation (potentially including bacterial, viral, fungal and parasitic origin) when full receptor occupancy has been achieved.

Corporate Confidential Information

In addition, subjects will have adequate preformed antibody to maintain protective humoral response for extended periods of time (months). Subjects enrolled in this study will be carefully monitored for signs and symptoms of an infection.

Corporate Confidential Information

Although not expected in this clinical study, the investigator will monitor for signs, symptoms and laboratory results consistent with clinically significant inflammation as well as for changes in renal function and signs of acute kidney injury as per local practice.

There has been no evidence that CFZ533 has an effect on clinical coagulation parameters, and no evidence from preclinical or clinical studies that CFZ533 presents an increased risk of thromboembolic events (TE).

Corporate Confidential Information

Nevertheless, standard coagulation parameters and TEs will be carefully monitored throughout the study.

The overall risk-benefit supports further investigation in patients with autoimmune diseases such as MG patients. However, there may be unknown risks of CFZ533 which may be serious and unforeseen.

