#### **8.4.7 Other safety evaluations**

All occurrences of infections must be carefully monitored by the investigator. Significant findings, which meet the definition of infection, must be recorded in the eCRF.

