### Adverse events

All information obtained on adverse events will be displayed by treatment and subject.

The number and percentage of subjects with adverse events will be tabulated by body system and preferred term with a breakdown by treatment. A subject with multiple adverse events within a body system is only counted once towards the total of this body system.

Corporate Confidential Information

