8.1.2 Descriptive analyses

All safety analyses will be performed on the safety analysis set; patients will be analyzed as treated.

Subject demographics and other baseline characteristics

All data for background and demographic variables will be listed by treatment group and subject. Summary statistics will be provided by treatment group.

Relevant medical history, current medical conditions, results of laboratory screens, drug tests and any other relevant information will be listed by treatment group and subject.

Treatment

Data for study drug administration, rescue medication and concomitant therapies will be listed by treatment group and subject.

Vital signs

All vital signs data will be listed by treatment, subject, and visit/time and if ranges are available abnormalities (and relevant orthostatic changes) will be flagged. Summary statistics will be provided by treatment and visit/time.

ECG evaluations

All ECG data will be listed by treatment, subject and visit/time, abnormalities will be flagged. Summary statistics will be provided by treatment and visit/time.

Clinical laboratory evaluations

All laboratory data will be listed by treatment, subject, and visit/time and if normal ranges are available abnormalities will be flagged. A separate listing is provided presenting all parameters in a subject with any abnormal values. Summary statistics will be provided by treatment and visit/time.

Adverse events

All information obtained on adverse events will be displayed by treatment and subject.

The number and percentage of subjects with adverse events will be tabulated by body system and preferred term with a breakdown by treatment. A subject with multiple adverse events within a body system is only counted once towards the total of this body system and treatment.

Serum total immunoglobulin G (IgG) and M (IgM)

Serum total IgG and IgM and percentage change from baseline will be listed by subject and visit/time. No descriptive summary statistics will be provided.

Immunogenicity

All immunogenicity results will be listed by subject and visit/time. No descriptive summary statistics will be provided.

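### Infections are the adverse event of special interest, but the visible plan compares arms only by crude percentage of subjects, with no time window, episode count or patient-time

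*Protocol*

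**What the plan says.** Three places in the protocol single out infection. The design section (text under Figure 3-1) says "Adverse Events (AEs) will be monitored throughout the study duration with special interest to infections". Section 3.6 says "Subjects treated with CFZ533 may be at an increased risk of infection". Section 8.4.7 asks investigators to watch all infections closely and adds "Significant findings, which meet the definition of infection, must be recorded in the eCRF". Section 2.1 makes safety and tolerability a primary objective.

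The analysis text is general. Protocol 11.5.2 says "The number and percentage of subjects with adverse events will be tabulated by body system and preferred term with a breakdown by treatment", followed by "A subject with multiple adverse events within a body system is only counted once towards the total of this body system". SAP 8.1.2 keeps the same rule: "A subject with multiple adverse events within a body system is only counted once towards the total of this body system and treatment". It also provides listings: "All information obtained on adverse events will be displayed by treatment and subject". SAP 7.1.1 describes the safety analysis as descriptive.

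On timing, protocol 3.1 says "The treatment period (24 weeks) will be followed by a safety follow-up period of other 24 weeks". Neither document says which part of those 48 weeks the adverse event table covers. The visible text contains no infection-specific table, episode count, patient-time or split by period.

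**The concern.** Infections recur, and these patients are already on background immunosuppression. Counting subjects once has two effects. A patient with one cold and a patient with five infections contribute equally. And the longer the window, the closer both arms move towards 100%, which compresses the contrast between them. If the window also includes weeks when the drug no longer acts, an increase confined to treatment is diluted further.

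At stake is how clearly the study report can describe the one risk the protocol names in advance. Listings show repeat infections patient by patient, but they do not compare the arms.

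**Working it through.** **Inputs from the documents.** 24 weeks of treatment and 24 weeks of follow-up (protocol 3.1); 22 patients per arm (protocol 11.6). The plan gives no infection figure to reproduce. Its total of 44 does reproduce: 36 × 1.20 = 43.2, rounded up to 44. (36 / 0.80 would give 45.)

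**Assumptions, because the documents are silent.** Placebo rate r infections per patient-year; a true doubling on CFZ533 during treatment; a tail of t further weeks after Week 25 in which the doubling continues; Poisson counts; no dropout; a table covering all 48 weeks.

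**Formulas.** Expected infections per patient over 48 weeks:

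- placebo: m0 = r × 48/52
- CFZ533: m1 = r × [2 × (24 + t) + (24 − t)]/52
- percentage with at least one infection: 1 − exp(−m)

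**Worked case, r = 1, t = 0.** m0 = 0.923, giving 60.3%. m1 = 72/52 = 1.385, giving 75.0%. The ratio is 75.0/60.3 = 1.24 and the difference 14.7 points.

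The attenuation has two sources. If subjects are counted once but only over the 24 treatment weeks, the figures are 1 − exp(−0.462) = 37.0% and 1 − exp(−0.923) = 60.3%, a ratio of 1.63. So counting once takes the ratio from 2.0 to 1.63, and adding the follow-up weeks takes it from 1.63 to 1.24.

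**Range.** The last two columns come from simulation (20,000 trials per case). They give the share of trials in which the lower limit of a 90% interval excludes no difference, first for the 48-week percentages and then for the mean on-treatment episode count (unequal-variance t statistic). With no drug effect, both are about 5%.

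| Placebo rate per patient-year | Tail after Week 25 | CFZ533 v placebo, at least one infection in 48 weeks | Ratio | Detected: percentage table | Detected: on-treatment episodes |
|---|---|---|---|---|---|
| 0.2 | none | 24% v 17% | 1.43 | 16% | 20% |
| 0.2 | 12 weeks | 28% v 17% | 1.64 | 23% | 20% |
| 0.5 | none | 50% v 37% | 1.35 | 21% | 36% |
| 1 | none | 75% v 60% | 1.24 | 28% | 57% |
| 1 | 12 weeks | 80% v 60% | 1.33 | 44% | 57% |
| 1 | 24 weeks | 84% v 60% | 1.40 | 58% | 57% |
| 2 | none | 94% v 84% | 1.11 | 27% | 82% |
| 2 | 24 weeks | 97% v 84% | 1.16 | 48% | 83% |

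Simulated shares are good to about one point. With between-patient heterogeneity (gamma variance 0.5, no tail), detection is about 20% v 46% at rate 1 and 20% v 63% at rate 2.

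On the absolute scale with no tail, the loss at rate 0.2 is negligible: 7.3 points over 48 weeks against 8.0 on treatment. At rate 2 it is large: 9.5 points against 23.9.

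**The case against.** The strongest reply is that the plan does not say what the arithmetic assumes. A reader might infer that the table pools treatment and follow-up by rule. No such rule is stated; the 48-week window is inferred from silence. Protocol text directly after the adverse event paragraph is redacted, and the SAP modules holding table shells and derivations (M7, M8) are not among the documents. What stands is that the window is not defined in the visible methodology.

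A reader might also infer that half the observation time is off drug and that a real rise would be largely hidden. The documents do not support this in general. No half-life is visible, and contraception is required for 12 weeks after the last dose, so some persistence is plausible. As the table shows, a full 24-week tail closes the detection gap at rate 1. At rate 0.2 with a 12-week tail the percentage table does slightly better. Low rates are the relevant case for serious or opportunistic infections.

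A third inference is that early leavers, counted as infection-free once unobserved, push the result towards no difference. This was not simulated, and the direction depends on which arm loses more patients.

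Other safeguards exist: preferred-term rows, full listings, regular DMC review, and a study hold after two severe systemic or opportunistic infections. They are useful, but they do not give a by-arm summary of infection frequency. Finally, the study is non-confirmatory and its safety analysis descriptive, so detection shares only measure visibility; no such test is planned. The simulated comparator was a t statistic, not the rate model proposed below.

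**Conclusion.** The point holds in a limited form. The protocol singles out infections, and the visible plan summarises them by arm only as a once-per-subject percentage with no window, episode count or patient-time.

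If infections are moderately frequent (about 1 per patient-year or more) and the effect fades after treatment, a true doubling is attenuated to a ratio of 1.24 or less. The table would also reveal it in about half as many trials as an on-treatment episode comparison, or fewer. Both conditions are assumptions. At low rates the loss is small. If the effect persists through follow-up, the detection loss disappears at rate 1, though the percentage ratio (1.40) still understates a rate ratio of 2.

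The documents do not show that harm would be concealed or the safety conclusion biased. Protocol 3.6 says the risk may increase, not that an increase is expected. Sample size remains a major limit: with heterogeneity, even the episode comparison misses a doubling in 37% to 54% of trials at rates 2 and 1. This is a cheap improvement to the analysis plan.

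**What to change.** Keep the existing adverse event table. Add to SAP 8.1.2 one descriptive infection table by arm, covering the MedDRA class Infections and infestations and its serious or severe subset. For each arm give:

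- patients with at least one infection
- number of episodes
- patient-years at risk
- episodes per patient-year, with a rate ratio or difference and 90% CI that allows for overdispersion (negative binomial or robust variance, with log patient-time as offset)

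Report first dose to Week 25, Week 25 to end of study, and overall. State the window of the existing table as well.

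The cost is SAP wording and one extra table. Protocol 9.1 already collects dates, severity and seriousness. Design and sample size do not change. Intervals will be wide at 22 per arm, and the model may not be estimable for the sparse subset, where counts and patient-years are enough. A Week 25 cut-off ignores any post-dose tail, which is why both periods and the total should be shown.

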### 3.2 Rationale for study design

In this study, a randomized, double-blind approach will be used to eliminate potential bias on safety and clinical efficacy data. Patients will be randomized to IV CFZ533 or IV placebo in a 1:1 ratio.

Placebo will be used as comparator to provide objective evidence of safety and efficacy data from patients exposed to the experimental therapy. Use of placebo will be in addition to standard of care therapy so as not to leave patients without established treatment.

For patients that are receiving corticosteroids at baseline, a predefined steroid tapering ([Table 6-1](#)) will be allowed after achievement of minimal manifestations state ([Jaretzki et al 2000](#)). The steroid tapering is instituted to follow the common medical practice in MG to minimize steroid exposure and to mirror standard of care. The proportion of patients who are intolerant to steroid taper in the CFZ533 vs the placebo arm will be a secondary endpoint.

This study will use the Quantitative Myasthenia Gravis score (QMG) and MG Composite score (MGC) as key efficacy outcome measures. Both the scores are established and validated efficacy measure in MG trials ([Jaretzki et al 2000](#), [Howard et al 2013](#), [Burns et al 2010](#)) and therefore assumed sufficiently sensitive to provide preliminary evidence for efficacy after 24 weeks of treatment. This timeframe is consistent with previous trials of MG therapeutics in similar target populations ([Howard et al 2013](#), [Muscle Study Group 2008](#)).

### **3.3 Rationale for dose/regimen, duration of treatment**

Corporate Confidential Information

**Safety and tolerability confirmed in humans:** A Phase 1 study (CCFZ533X2101), testing single ascending doses (0.03 to 10 mg/kg) of CFZ533 IV and 3 mg/kg SC, is currently ongoing. Safety and tolerability data are presented in [Section 1.1.1.3](#) Based on clinical experience so far, the 10 mg/kg IV q4w dosing regimen is anticipated to be safe and tolerable in MG patients.

Corporate Confidential Information

### **3.4 Rationale for choice of comparator**

In this study, placebo will be used as comparator to provide objective evidence of safety and efficacy data from patients exposed to the experimental therapy. Patients should remain on their standard of care therapies and dose maintained at a constant level during the study ([Section 6.10](#)).

Corporate Confidential Information

### 3.6 Risks and benefits

It is not known if there could be a benefit to patients from treatment with CFZ533.  
Corporate Confidential Information

Corporate Confidential Information

The risk to subjects in this trial will be minimized by adherence to the inclusion/exclusion criteria, close clinical monitoring, and targeted monitoring/follow-up visit safety assessments.

Corporate Confidential Information

Hypersensitivity or infusion reactions can manifest with itching, flushing, headache, nausea/vomiting, hypotension, urticaria, bronchospasm, or angioedema. No such events were found in the Phase 1 study with CFZ533. In this study, CFZ533 will be administered as a 2-hour infusion where such hypersensitivity reactions can still occur. Subjects will be monitored up to 4 hours after the end of the infusion at each visit.

Subjects treated with CFZ533 may be at an increased risk of infection.  
Corporate Confidential Information

Administration of CFZ533 is expected to result in immunosuppression, with a decreased capacity to mount a response to novel immunogens requiring T cell-dependent B cell activation (potentially including bacterial, viral, fungal and parasitic origin) when full receptor occupancy has been achieved.

Corporate Confidential Information

In addition, subjects will have adequate preformed antibody to maintain protective humoral response for extended periods of time (months). Subjects enrolled in this study will be carefully monitored for signs and symptoms of an infection.

Corporate Confidential Information

Although not expected in this clinical study, the investigator will monitor for signs, symptoms and laboratory results consistent with clinically significant inflammation as well as for changes in renal function and signs of acute kidney injury as per local practice.

There has been no evidence that CFZ533 has an effect on clinical coagulation parameters, and no evidence from preclinical or clinical studies that CFZ533 presents an increased risk of thromboembolic events (TE).

Corporate Confidential Information

Nevertheless, standard coagulation parameters and TEs will be carefully monitored throughout the study.

The overall risk-benefit supports further investigation in patients with autoimmune diseases such as MG patients. However, there may be unknown risks of CFZ533 which may be serious and unforeseen.

A maximum of approximately 600 mL of blood is planned to be collected over a period of 52 weeks (including screening, treatment and follow up period) from each subject as part of the study. Additional samples for monitoring of any safety findings would be in addition to this. This is not considered to be a risk for this population.

## **4 Population**

A total of approximately 44 subjects will be enrolled in the study and randomized. At least 36 subjects are expected to complete the study.

Subject selection is to be established by checking all eligibility criteria at screening (Visit 1) and before randomization (Visit 3). A relevant record (e.g. checklist) of the eligibility criteria must be stored with the source documentation at the study site. No additional criteria should be applied by the investigator, in order that the study population will be representative of all

eligible subjects. Deviation from **any** entry criterion excludes a subject from enrollment into the study.

#### 4.1 Inclusion criteria

Patients eligible for inclusion in this study have to fulfill all of the following criteria:

1. Able to provide signed informed consent.
2. 18-85 year old male or female patients.
3. Body mass index of 18-40 kg/m^2.
4. Diagnosis of MG class IIa to IVa inclusive (Myasthenia Gravis Foundation of America Clinical Classification).
5. Quantitative Myasthenia Gravis (QMG) score of 10 or greater. If the QMG score is < 15, no more than 4 points may be derived from items 1 or 2 (ocular motility disturbance and ptosis).
6. Presence of acetylcholine receptor (AChR) or Muscle Specific Kinase (MuSK) autoantibodies based on medical history and confirmed by autoantibodies diagnostic test performed at screening.
7. Only one immunosuppressant or immunomodulatory drug at a stable dose is allowed during the study (i) azathioprine and mycophenolate mofetil must be stable for at least 4 months prior to randomization (ii) cyclosporine must be stable for at least 3 months prior to randomization.
8. If the patient is on oral corticosteroids, methotrexate or tacrolimus at screening, the dose must be stable for at least 1 month prior to randomization.
9. If the patient is on cholinesterase inhibitors at screening, the dose must be stable for at least 2 weeks prior to randomization.
10. Women of child-bearing potential, defined as all women physiologically capable of becoming pregnant, may be included in the study if they are using highly effective methods of contraception during the study and for 12 weeks after study treatment.
11. Highly effective contraception methods include:
  - Total abstinence (when this is in line with the preferred and usual lifestyle of the subject). Periodic abstinence (e.g., calendar, ovulation, symptothermal, post-ovulation methods) and withdrawal are not acceptable methods of contraception.
  - Female sterilization (have had surgical bilateral oophorectomy with or without hysterectomy) or tubal ligation at least six weeks before taking study treatment, confirmed by medical documentation. In case of oophorectomy alone, only when the reproductive status of the woman has been confirmed by follow up hormone level assessment.
  - Male sterilization (at least 6 months prior to screening, with the appropriate post-vasectomy documentation of the absence of sperm in the ejaculate). For female subjects on the study the vasectomized male partner should be the sole partner for that subject.

- Combination of any two of the following (a+b or a+c, or b+c):
  - a. Use of oral, injected or implanted hormonal methods of contraception or other forms of hormonal contraception that have comparable efficacy (failure rate <1%), e.g. hormone vaginal ring or transdermal hormone contraception.
  - b. Placement of an intrauterine device (IUD) or intrauterine system (IUS).
  - c. Barrier methods of contraception: condom or occlusive cap (diaphragm or cervical/vault caps). For UK: with spermicidal foam/gel/film/cream/vaginal/suppository
- In case of use of oral contraception, women should have been stable on the same pill for a minimum of 3 months before taking study treatment.

Women are considered post-menopausal and not of child bearing potential if they have had 12 months of natural (spontaneous) amenorrhea with an appropriate clinical profile (e.g., age appropriate, history of vasomotor symptoms) or have had surgical bilateral oophorectomy (with or without hysterectomy), total hysterectomy or tubal ligation at least six weeks ago. In the case of oophorectomy alone, only when the reproductive status of the woman has been confirmed by follow up hormone level assessment is she considered not of child bearing potential.

